### 1050 **5.2 Adverse Events**

#### 1051 **5.2.1 Reportable Adverse Events**

1052 Because study treatment with bifocal or single-vision spectacles is non-invasive and consistent  
1053 with usual care, it is not expected that there would be any significant adverse events other than  
1054 those already being captured as part of clinical outcome assessments (e.g., treatment failure  
1055 criteria). For this reason, only serious, related adverse events shall be reported to the  
1056 Coordinating Center, on the applicable eCRF, within seven (7) days of identification.  
1057 Furthermore, investigators must still abide by IRB reporting requirements. If covered by the  
1058 JCHR IRB, investigators are required to report all serious, related adverse events to the JCHR  
1059 IRB within seven (7) calendar days of identification of the event.

### 1060 **5.3 Safety Oversight**

1061 A Data and Safety Monitoring Committee (DSMC) will review compiled safety data at periodic  
1062 intervals, with a frequency of no less than twice a year. The DSMC can request modifications to  
1063 the study protocol or suspension or outright stoppage of the study if deemed necessary based on  
1064 the totality of safety data available. Details regarding DSMC review will be documented in a  
1065 separate DSMC charter.

1066 The objective of the DSMC review is to decide whether the study (or study treatment for an  
1067 individual or study cohort) should continue per protocol, proceed with caution, be further

1068 investigated, be discontinued, or be modified and then proceed. Suspension of enrollment (for a  
1069 particular group, a particular study site, or for the entire study) is a potential outcome of a DSMC  
1070 safety review.

1071 **5.4 Stopping Criteria**

1072 The study may be discontinued by the Steering Committee (with approval of DSMC) prior to the  
1073 preplanned completion of follow-up for all study participants. No formal guidelines for stopping  
1074 the study for futility or efficacy are pre-specified (section 7.4).

1075 **5.5 Participant Discontinuation of Study Treatment**

1076 Rules for discontinuing study treatment use are one of the following:

- 1077 • The investigator believes it is unsafe for the participant to continue to receive the  
1078 treatment.  
1079 • The participant or parent requests that the treatment be stopped.

1080 Even if the study treatment is discontinued, the participant will be encouraged to remain in the  
1081 study through the 38-month Secondary Outcome Visit.

1082

## Chapter 6: Miscellaneous Considerations

1083 **6.1 Contacts by the Jaeb Center for Health Research and Sites**

1084 The Jaeb Center serves as the PEDIG Coordinating Center. The Jaeb Center will be provided the  
1085 parents' contact information. The Jaeb Center may contact the parents of the participants.  
1086 Permission for such contacts will be included in the Informed Consent Form. The principal  
1087 purpose of the contacts will be to develop and maintain rapport with the participant's family and  
1088 to help coordinate the scheduling of study visits, when needed.

1089 **6.2 Participant Compensation**

1090 Participant compensation will be specified in the informed consent form.

1091 **6.3 Cost of Spectacles**

1092 Spectacles required as part of the study will be paid for by the study. Spectacle changes are  
1093 required following a cycloplegic refraction that indicates the spectacles are out of study tolerance  
1094 limits, at the time of failure for children in the SVL group, and at the 36-month Primary  
1095 Outcome Visit for the SVL group. Spectacles may be updated and paid for by the study  
1096 whenever a spectacle change is required or made at investigator discretion for both treatment  
1097 groups. Spectacles may be replaced and paid for by the study if in poor condition (e.g.,  
1098 significantly scratched lenses, broken frame) at any time during follow-up.

1099 At the parent's request, a separate prescription for SVL sports glasses may be provided for wear  
1100 during sports. Sports glasses will not be paid for by the study. Sports glasses must only be worn  
1101 when playing sports.

1102 **6.4 Participant Withdrawal**

1103 Participation in the study is voluntary and a participant may withdraw at any time. For  
1104 participants who withdraw, their data collected prior to their withdrawal will be used. This  
1105 stipulation is specified in the consent form.

1106 **6.5 Confidentiality**

1107 For security and confidentiality purposes, participants will be assigned an identifier that will be  
1108 used instead of their name. Protected health information gathered for this study will be shared  
1109 with the coordinating center, the Jaeb Center for Health Research in Tampa, FL. De-identified  
1110 participant information may also be provided to research sites involved in the study.

1111

## Chapter 7: Statistical Considerations

### 1112 7.1 Statistical and Analytical Plans

1113 The approach to sample size calculation and statistical analyses are summarized below.

### 1115 7.2 Primary Objective and Hypothesis

1116 The primary objective is to determine if participants with ET greater at near who are prescribed  
1117 SVLs and BFLs have different failure probabilities by 36 months.

1118 The primary outcome is treatment failure by 36 months, defined as meeting any one of the  
1119 following criteria at any follow-up visit from 3 months to 36 months inclusive:

- 1120 1. Constant ET  $\geq 15\Delta$  by SPCT at distance. (NOTE: intermittent ET and esophoria of any  
1121 magnitude are NOT considered failures.)
- 1122 2. Decrease in near stereoacuity on the Randot Preschool Stereoacuity (RPS) Test of 2 or  
1123 more levels from baseline, or from 960" at baseline to nil (see Table 2 in section 3.5 for  
1124 reference).
  - 1125 • At follow-up visits, the best of two stereoacuity measures in OFFICE spectacles  
1126 will be used.
  - 1127 • Baseline stereoacuity is defined as the near stereoacuity recorded with +3.00 D  
1128 power added to the participant's enrollment distance spectacle correction in trial  
1129 frames.
  - 1130 • Approximately 50% of participants are expected to have nil near stereoacuity at  
1131 baseline; it is acknowledged that these participants will not be able to meet the  
1132 near stereoacuity failure criteria.
- 1133 3. Binocular diplopia with a frequency of "more than 2 times per day" over the last week at  
1134 distance or near, by parental report.

1135 If nonsurgical or surgical treatment for ET other than the randomized treatment is before meeting  
1136 failure criteria, that participant will be considered a failure at the visit that such treatment is  
1137 prescribed.

1138 The study is designed as a superiority study to evaluate a 2-sided primary null hypothesis that the  
1139 failure probability by 36 months is the same between the SVL and BFL groups versus the  
1140 alternative hypothesis that it is different:

1142

1143  $H_{\text{null}}$  BFL% of failure by 36 months = SVL% of failure by 36 months

1144

$H_{\text{alternative}}$  BFL% of failure by 36 months  $\neq$  SVL% of failure by 36 months

1145

1146 The composition of the treatment failures (i.e., whether due to distance motor failure, near  
1147 stereoacuity failure, or diplopia "more than 2 times per day" over the last week) is also of  
1148 primary interest. However, the failure criteria may be interrelated and thus there is no specific  
1149 hypothesis for each criterion.

1150

### 1151 7.3 Sample Size

1152 Sample size estimation is based on data from the retrospective cohort study conducted by  
1153 Whitman et al. After approximately 4 years of follow-up, 15.6% of the BFL group and 3.9% of

1154 the SVL group underwent strabismus surgery, all of whom had an increase in the distance angle  
 1155 of deviation to more than  $10\Delta$  by PACT (average increase from baseline was  $25\Delta$  in the BFL  
 1156 group and  $20.5\Delta$  in the SVL group). In the current study, the primary outcome is based on  
 1157 distance motor failure (based on SPCT), near stereoacuity failure, or diplopia “more than 2 times  
 1158 per day” over the last week by 36 months. Given a shorter follow-up, the proportion of distance  
 1159 motor failures may be less than that found in the Whitman et al. study. The proportion of near  
 1160 stereoacuity failures is believed to be less in the BFL group than the SVL group, but no data are  
 1161 available to provide estimates of the failure proportion for each group.  
 1162

1163 Table 4 shows the sample size estimates under various assumptions for the primary outcome in  
 1164 the SVL group and the difference in the primary outcome between the BFL and SVL groups. To  
 1165 be conservative, the total sample size needed to detect a treatment group difference is calculated  
 1166 using a two-sided Pearson chi-square test with a type I error rate of 5% and 90% power. Power is  
 1167 expected to increase slightly using a time-to-event approach for the primary outcome analysis.  
 1168

1169 **Table 4. Total sample size needed to detect a treatment group difference in proportions of  
 1170 failure by 36 months under various assumptions**

% of Failure in SVL Group	Treatment Group Difference in % of Failures (BFL – SVL)							
	5%	6%	7%	8%	9%	10%	15%	20%
3%	870	656	518	424	356	306	172	116
4%	1018	756	592	480	400	342	186	124
5%	1164	856	664	534	442	376	202	130
6%	1304	954	734	588	484	408	214	138
7%	1442	1140	802	640	524	440	228	146
8%	1576	1140	870	690	564	472	242	152
9%	1708	1230	936	740	602	502	254	158
10%	1836	1318	998	788	640	532	266	164
11%	1960	1402	1060	834	676	562	278	172
12%	2082	1486	1120	880	712	590	290	178
13%	2198	1566	1178	924	746	618	302	182
14%	2314	1644	1236	966	780	644	312	188
15%	2424	1720	1290	1008	812	670	322	194

1171  
 1172 Assuming a failure probability of 5% in the SVL group and 15% in the BFL group, a sample size  
 1173 of 376 (188 per group) provides 90% power to detect a treatment group difference with a two-  
 1174 sided type I error rate of 5%. The total sample size is increased to 444 (222 per group) to account  
 1175 for up to a 15% loss to follow-up over 36 months.

#### 1176 **7.4 Interim Monitoring**

1177 An interim sample size re-estimation based on 12-month treatment failure outcome was  
 1178 considered because of uncertainty in the assumed proportions of failure by 36 months in the

1179 treatment groups. However, it is unclear how well the 12-month outcome will predict the 36-  
1180 month outcome. Because of this additional uncertainty, this approach will likely increase the bias  
1181 in the estimation of the 36-month primary outcome. To minimize this bias, sample size re-  
1182 estimation would have to be performed based on the partial 36-month outcome data, but it would  
1183 be too late to affect recruitment since recruitment is expected to be completed within 3 years. In  
1184 addition, the estimated total sample size of 444 is close to the maximum number of eligible  
1185 participants that could potentially be recruited. Therefore, a sample size re-estimation will not be  
1186 performed.

1187 Interim monitoring for futility and/or efficacy was also considered. For the same reasons, interim  
1188 monitoring would have to be conducted based on the partial 36-month outcome data when  
1189 recruitment is likely completed. Even if there is evidence for futility and/or efficacy for the  
1190 primary outcome at that time, the remaining follow-up visits would likely be continued to collect  
1191 data on all the outcomes including binocular function at 38 months. Therefore, there will be no  
1192 formal guidelines for stopping the trial for futility or efficacy. The DSMC will review safety and  
1193 efficacy data periodically.

## 1194 **7.5 Analysis Dataset**

1195 The primary efficacy analysis will follow an intent-to-treat (ITT) principle. All randomized  
1196 participants will be included in the primary analysis dataset and analyzed according to the group  
1197 they were originally assigned, regardless of what treatment (if any) they received.

## 1198 **7.6 Analysis of Primary Outcome – Treatment Failure by 36 Months**

1199 There may be participants who are lost to follow-up before their 36-month primary outcome data  
1200 are collected. To use the data collected from these participants before they are lost to follow-up,  
1201 a time-to-event analysis will be performed for the primary outcome. For participants who meet  
1202 failure criteria before or at the 36-month Primary Outcome Visit, time to treatment failure will be  
1203 defined as the time from randomization to the visit at which the failure is confirmed (either at the  
1204 initial visit or later at a Failure Confirmation Visit because the spectacle correction must be  
1205 updated [section 3.6]). If a participant is prescribed non-randomized treatment for ET before  
1206 meeting failure criteria, they will be considered a failure at the time when such treatment is  
1207 prescribed. Participants lost to follow-up are considered censored at the time of their last  
1208 recorded visit. If a participant is lost to follow-up before failure is confirmed, they will be  
1209 censored at their last visit for the primary analysis.

1210 The hazard ratio of treatment failure for treatment with BFLs versus SVLs and a two-sided 95%  
1211 confidence interval (CI) will be estimated with a Cox proportional hazards model. The model  
1212 will be adjusted for baseline near stereoacuity by the Randot Preschool Stereotest (RPS) in +3.00  
1213 D trial frames and baseline magnitude of the distance esodeviation by SPCT. The treatment  
1214 group difference in the probability of failure and a two-sided 95% CI will be estimated using the  
1215 direct adjustment method. The proportional hazards and functional form assumptions will be  
1216 evaluated.

1217 The timing and composition of failures (distance motor, near stereoacuity, diplopia, starting non-  
1218 protocol treatment) will be tabulated by treatment group to aid in the interpretation of the  
1219 treatment group difference for failure probability by 36 months.

1220 **7.6.1 Sensitivity Analyses for Primary Outcome**

1221 As a sensitivity analysis, if a participant meets the failure criteria prior to a required spectacle  
1222 update but is lost to follow-up before the failure is confirmed, the participant will be treated as a  
1223 failure at the time when they initially met the failure criteria (suspected failure). The primary  
1224 analysis will be repeated with these unconfirmed failures being counted as failures.

1225 As an additional sensitivity analysis, treatment crossovers (BFL group participants who have  
1226 bifocals formally discontinued and begin to wear SVL; SVL group participants prescribed  
1227 bifocals) that occur before meeting any of the clinical measures for failure will be censored at the  
1228 visit date when treatment crossover occurred.

1229 **7.6.2 Contingency Plan for Primary Outcome**

1230 If the assumptions for the Cox model are not satisfied, an exact logistic regression model with  
1231 the same covariates will be attempted. If the adjusted model fails to converge, a model will be fit  
1232 without the adjustment for covariates. If the exact logistic regression still fails to converge,  
1233 Barnard's exact test will be performed.

1234 **7.7 Analysis of Secondary Outcomes**1235 **7.7.1 Binocular Function Test Score in BFLs at the Secondary Outcome Visit**

1236 A secondary outcome is the binocular function test score at the Secondary Outcome Visit (Post-  
1237 failure Secondary Outcome visit if failed or 38-month Secondary Outcome Visit if not failed).  
1238 The test score is assigned on an ordinal scale that combines the results of the RPS test, Random  
1239 Dot Stereo Butterfly test, and Preschool Worth 4-shape (W4S) test that were measured using the  
1240 bottom portion of the participants' BFLs. Given that BFLs can potentially reduce the magnitude  
1241 of near ET, which might in turn improve near stereoacuity, it was felt critical to measure  
1242 binocular function after a period of BFL wear in both treatment groups. Consequently, after 36  
1243 months of SVL or BFL wear, the SVL group will be prescribed BFLs, the BFL group will  
1244 continue wearing their BFLs, and both groups will be re-assessed at the 38-month Secondary  
1245 Outcome Visit. Because participants who meet failure criteria for the primary outcome at a prior  
1246 visit must be released to treatment at investigator discretion, these participants will be prescribed  
1247 BFLs (if in the SVL group) or continue in BFL (if in the BFL group) and return within 2 months  
1248 after meeting failure criteria for a Post-failure Secondary Outcome Visit.

1249 The possible levels of binocular function will be 48, 72, 120, 240, 480, 960 arcsec (RPS test),  
1250 2400 arcsec (Random Dot Stereo Butterfly test), and 10,000 or 100,000 arcsec (fusion or  
1251 suppression, respectively, indicated by Preschool W4S test). The binocular function test score  
1252 will be calculated by converting binocular function to a log value ranging from 1.68 (log of 48  
1253 arcsec) to 5.0 (log of 100,000 arcsec). Baseline near stereoacuity on the RPS test that was  
1254 measured through +3.00 D lenses will be used in the calculation of the binocular function test  
1255 score at baseline, and the Random Dot Stereo Butterfly and Preschool W4S tests that were also  
1256 measured through +3.00 lenses. The score at the Secondary Outcome Visit (Post-failure  
1257 Secondary Outcome visit if failed or 38-month Secondary Outcome Visit if not failed) and the  
1258 change from baseline will be tabulated for each treatment group. A treatment group comparison  
1259 of the scores will be performed using the exact Wilcoxon rank sum test to determine whether the  
1260 treatment groups have different distributions of the score. If the hypothesis test for the primary  
1261 outcome is significant, an alpha of 0.05 will be passed down to this test. If not, this outcome will  
1262 be exploratory with no *P*-value reported.

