### 3.1 Study Follow-up Visits

420

Participants randomized in the study generally\* will return for follow-up according to the following schedule (timed from randomization, unless otherwise specified):

422

Protocol-specified Visit/Call	Target Day	Target Window (around target day)	Allowable Window (around target day)
1-month call	Randomization+30 days	± 1 week 23 to 37 days	1 to 76 days
3-month visit	Randomization+91 days	± 2 weeks 77 to 105 days	± 1.5 months 46 to 137 days
6-month visit	Randomization+183 days	± 2 weeks 169 to 197 days	± 1.5 months 138 to 228 days
9-month visit	Randomization+274 days	± 2 weeks 260 to 288 days	± 1.5 months 229 to 320 days
12-month visit	Randomization+365 days	± 2 weeks 351 to 379 days	-1.5 to +3 months 321 to 457 days
18-month visit	Randomization+548 days	± 2 weeks 534 to 562 days	± 3 months 458 to 639 days
24-month visit	Randomization+731 days	± 2 weeks 717 to 745 days	± 3 months 640 to 822 days
30-month visit	Randomization+913 days	± 2 weeks 899 to 927 days	± 3 months 823 to 1004 days
36-month Primary Outcome Visit b	Randomization+1096 days	± 2 weeks 1068 to 1124 days	-3 to +6 months 1005 to 1278 days
38-month Secondary Outcome Visit c,d	36-month visit +60 days (or 38-months from randomization for confirmed failures occurring before 36 months).	± 4 weeks 32 to 88 days	-1 month to +6.5 months 30 to 258 days from 36-month Visit (from 38 months following randomization for confirmed failures)
Additional if needed	Target Day	Target Window (around target day)	Allowable Window (around target day)
1-month call after new spectacles e	Visit at which spectacles changed +30 days	± 1 week 23 to 37 days	1 to 76 days
Failure Confirmation Visit f	Visit at which failure criteria met and spectacles updated + 60 days	± 4 weeks 46 to 88 days	30 days to open end (must be completed)
Post-failure Secondary Outcome Visit g	Visit at which failure confirmed +60 days	± 4 weeks 32 to 88 days	-1 month to +6.5 months 30 to 258 days from confirmed failure

b SVL group is prescribed BFLs at end of the 36-month Primary Outcome Visit. The exception is participants who previously failed, had the post-failure secondary outcome visit, and been released to treatment.

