### 619 **3.5 Failure Criteria**

620 Treatment failure is defined as meeting one or more of the following criteria at any follow-up  
621 visit between 3 months to 36 months inclusive:

- 622 1. Constant ET  $\geq 15\Delta$  by SPCT at distance. (NOTE: intermittent ET and esophoria of any  
623 magnitude are NOT considered failures).
- 624 2. Decrease in near stereoacuity on the Randot Preschool Stereoacuity Test (at 33 cm) of 2  
625 or more levels from baseline (see levels below) stereo or from 960" (equivalent to 800"  
626 when measured at 40 cm) at baseline to nil (*criteria not applicable if nil near stereo at*  
627 *baseline*)
  - 628 • Baseline stereoacuity is defined as the near stereoacuity performed with +3.00 D  
629 added to the participant's enrollment distance spectacle correction in trial frames.
  - 630 • At all follow-up visits, the best of two stereo measures in the OFFICE lenses will be  
631 used to determine treatment failure.
  - 632 • Stereoacuity values are calculated for the 33 cm test distance required for testing  
633 through the added +3.00 D lenses at near (instead of the standard 40 cm). **NOTE:**  
634 Participants without measurable near stereoacuity at baseline cannot fail by  
635 stereoacuity criteria.

636  
637  
638**Table 2. Baseline and Follow-up Randot Preschool Stereoacuity Test Levels for Defining Treatment Failure**

Baseline Stereoacuity (in trial frames with lens power that is +3.00D more than distance correction) a	Follow-up Stereoacuity for Treatment Failure (best of two tests in OFFICE spectacles)
48" (40" at 40 cm)	120" or worse
72" (60" at 40 cm)	240" or worse
120" (100" at 40 cm)	480" or worse
240" (200" at 40 cm)	960" or worse
480" (400" at 40 cm)	Nil
960" (800" at 40 cm)	Nil
Nil	Not applicable

639  
640  
641  
642  
643  
644  
645  
646  
647  
648  
649  
650  
651  
652  
653  
654  
655  
656  
657  
658  
659  
660  
661  
662  
663  
664  
665  
666  
667  
The two sphere powers should be added and a single lens used for the spherical power component of the trial frames.

3. Binocular diplopia with a frequency of “more than 2 times per day” over the last week by parental report.
4. If any nonsurgical or surgical treatment for ET other than the randomized treatment is started before the participant meets failure criteria, the participant will be considered a failure at the visit at which the non-randomized treatment is prescribed.

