758        ○ Be prescribed BFLs if in the SVL group or continued in BFLs if in the BFL group  
759            (section 3.4.1)  
760        ○ Return in 2 months (window: 4 to 12 weeks) for their:  
761            • Post-failure Secondary Outcome Visit (section 3.7) if failure occurred prior to  
762              the 36-month Primary Outcome Visit or  
763            • 38-month Secondary Outcome Visit if failure occurred at the 36-month  
764              Primary Outcome Visit (section 3.8).

765     **3.7 Post-failure Secondary Outcome Visit (After Confirmed Failure)**

766     Post-failure Secondary Outcome Visits occur 2 months (window: 4 to 12 weeks) after a  
767     CONFIRMED failure at either a protocol-specified visit or a Failure Confirmation Visit. All  
768     testing procedures completed at the 38-month Secondary Outcome Visit (section 3.8) will be  
769     completed at this Post-failure Secondary Outcome Visit.

770     After a Post-failure Secondary Outcome Visit is completed:

- 771        • Further treatment is at investigator discretion (including whether to continue BFL or  
772            SVL spectacles).

773     **3.7.1 Treatment After the Post-failure Secondary Outcome Visit**

774     Participants with confirmed failure status (sections 3.5 and 3.6) who have completed a Post-  
775     failure Secondary Outcome Visit prior to 36 months may be prescribed treatment at investigator  
776     discretion. Note that office spectacles will no longer be prescribed.

777     **3.7.2 Follow-up After the Post-failure Secondary Outcome Visit**

778     Participants with confirmed failure status (sections 3.5 and 3.6) who have completed a Post-  
779     failure Secondary Outcome Visit prior to 36 months will return for follow-up at 12 months and  
780     24 months (with reduced testing as described below), and for the 38-month Secondary Outcome  
781     Visit (as described in section 3.8); all other study visits will be skipped.

782     At the 12- and 24-month visits, these participants will undergo the following (reduced) testing  
783     while wearing their habitual correction:

- 785        1. Monocular Visual Acuity Testing: Distance VA will be measured (right eye first) with the  
786            participant wearing habitual correction and without cycloplegia, using the same test method  
787            used at enrollment.
  - 788            • ATS-HOTV; e-ETDRS; OR crowded single-optotype or single-line HOTV, LEA  

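### Section 7.6 dates confirmed failures at the confirming visit, although failure is defined by the visit at which criteria are met; the reported difference by 36 months can shift by up to about 1 point in 10

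*Protocol*

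**What the plan says.** **Endpoint.** Section 3.5: "Treatment failure is defined as meeting one or more of the following criteria at any follow-up" visit from 3 to 36 months inclusive. Section 7.2 repeats this and states the null hypothesis that the "failure probability by 36 months is the same between the SVL and BFL groups versus the" alternative of a difference. Section 3.6 keeps the same logic for failures confirmed late: the child goes on to the "38-month Secondary Outcome Visit if failure occurred at the 36-month" visit, so the failure is attached to month 36 even though confirmation came afterwards.

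**Event time.** Section 7.6 counts everyone who meets criteria before or at the 36-month visit. It then sets the event time, "defined as the time from randomization to the visit at which the failure is confirmed", either on the spot or at a later Failure Confirmation Visit. Children lost before confirmation are censored at their last visit. A Cox model gives the hazard ratio, and direct adjustment gives the difference in failure probability with a 95% CI.

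**Sensitivity analysis.** Section 7.6.1 counts a child lost before confirmation as a "failure at the time when they initially met the failure criteria (suspected failure"), and repeats the primary analysis with these children added.

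**Calendar.** Section 3.1 puts the 36-month visit at day 1096. Its target window is printed as plus or minus "2 weeks 1068 to 1124 days" (the day range is actually plus or minus 28 days), and its allowable window, after a minus sign, as "3 to +6 months 1005 to 1278 days". The Failure Confirmation Visit is targeted 60 days after the suspected failure, with a 30-day minimum and no upper limit.

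**The concern.** The adjusted difference is the absolute effect the trial will report for failure by 36 months. The set of children who count as failures follows the visit definition, but the dates given to some of them lie beyond 36 months. If the Cox-based probabilities are evaluated at 36 months, those children count as not yet failed, and the figure no longer estimates the endpoint of sections 3.5 and 7.2.

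A second effect is internal to 7.6.1. Take two children who meet criteria at the same visit and both need new spectacles. The one who is later confirmed gets the confirmation date; the one who is lost gets the earlier, first-met date. Both enter the same model.

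**Working it through.** **1. Design figures.** For 5% vs 15%, two-sided 5%, 90% power (section 7.3):

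n = [1.960·√(2·0.10·0.90) + 1.282·√(0.05·0.95 + 0.15·0.85)]² / 0.10² = 187.05, so 188 per group (376). With 15% loss, 188/0.85 = 221.2, so 222 per group (444). Both agree with the protocol.

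**2. When is a 36-month failure dated late?** The earliest confirmation of a failure found in the printed target window is 1068 + 30 = day 1098, after day 1096. Under the 4-week minimum of section 3.5.2 it is 1068 + 28 = day 1096 itself. Only 36-month visits in the early part of the allowable window could be confirmed before day 1096 (1005 + 30 = day 1035). A failure found at the 30-month visit is not affected at normal delays: the latest allowable day, 1004, plus 88 is day 1092.

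**3. How much of the difference rests on the 36-month visit?** Assume a flat hazard (not in the protocol), with failures detected at the scheduled visits. Event-free probability at the 30-month target, day 913, with 913/1096 = 0.833:

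- BFL: 0.85^0.833 = 0.8734, so 0.8734 − 0.85 = 2.34 points are found at month 36.
- SVL: 0.95^0.833 = 0.9582, so 0.9582 − 0.95 = 0.82 points.
- Contribution to the difference: 2.34 − 0.82 = 1.52 of the 10 points.

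**4. Confirmation dating alone.** If a share c of these failures is confirmed after day 1096 and the difference is read there, the shortfall is c × 1.52. The protocol gives no value for c.

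| c | Shortfall (points) |
|---|---|
| 10% | 0.15 |
| 25% | 0.38 |
| 40% | 0.61 |

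**5. Scatter of the 36-month visit, if actual dates are used.** Let F be the share of 36-month visits held by day 1096. The conditional failure probability at that visit is q = 0.0234/0.8734 = 0.0268 (BFL) and 0.0082/0.9582 = 0.0085 (SVL). The protocol does not say when event-free completers are censored, so both options are shown, without any confirmation delay:

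- Completers stay at risk past day 1096: difference = 10 − 1.52·(1 − F).
- Completers censored at their own 36-month visit: event-free probability = S(913)·(1 − F)^q in each group.

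| 36-month visits | F | Completers at risk | Completers censored at visit |
|---|---|---|---|
| Late (uniform, −28 to +91 days) | 28/119 = 0.24 | 8.8 | 8.9 |
| Symmetric | 0.50 | 9.2 | 9.5 |
| Early (uniform, −56 to +28 days) | 56/84 = 0.67 | 9.5 | 10.1 |
| Earlier still | 0.80 | 9.7 | 10.9 |

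With scatter and confirmation together, the lowest case is late visits with half of failures needing confirmation and completers at risk: 10 − 1.52·(1 − 0.235·0.5) = 8.7.

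**6. Simulation.**

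- Unadjusted Kaplan-Meier (flat hazard, 15% loss, 0% to 50% needing confirmation): 8.8 to 9.8 points at day 1096 with symmetric, late or full-window visits, and 10.2 with early visits, completers censored at the visit and no confirmation delay. Visit-indexed timing gave 9.8 to 10.3.
- Adjusted Cox model with direct adjustment (1000 trials per scenario, 222 per arm, flat hazard, symmetric visits with or without a late tail, 0% to 40% needing confirmation): 8.9 to 9.7 at day 1096.
- Hazard ratio, over flat and rising hazards: 3.1 to 3.4, against 3.2 to 3.4 with nominal first-met dating. Power: 0.86 to 0.94, against 0.90 to 0.94.

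**7. First-met dating at nominal visits.** Events come before censorings at month 36: 0.8734·(1 − 0.0268) = 0.850 and 0.9582·(1 − 0.0085) = 0.950, a difference of 10.0 whatever the actual visit dates.

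**The case against.** **Much is left open, not fixed wrongly.** Section 7.6 names no reading day, no time unit and no censoring time for event-free completers. These commonly go to the analysis plan, which is not at hand, and actual days is only the natural reading. This stands: the scatter in step 5 is conditional on those choices. Confirmation dating is different. Section 7.6 states it as a rule, and an analysis plan using first-met dates would depart from the protocol.

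**Section 7.6 drops no qualifying failure.** It first decides who is an event, then assigns a time. This also stands, and is why the hazard ratio and test barely move. It does not help a probability read at 36 months.

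**Confirmation dating follows the clinical design.** When spectacles are out of tolerance, failure is not yet confirmed, and it may later be confirmed on a different criterion. That is a good reason to require confirmation before counting a failure. It does not settle the date, and section 3.6 itself attaches a late-confirmed failure to the 36-month visit.

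**Children in 7.6.1 have no confirmation date.** True; first-met is the only date available for them. The confirmed failures in the same model do have one, so two rules remain.

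**The need for confirmation may be small.** Section 3.3 requires a cycloplegic refraction, with updating if out of tolerance, at 30 months, so 40% may be high.

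**A stronger reading is tempting:** that the reported difference will always be too low. The documents do not support it. The allowable window opens at day 1005; with early visits and completers censored at that visit, the difference reads correctly or too high.

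**Conclusion.** The point holds as a minor one. Section 7.6 fixes an event date that does not match the visit-defined endpoint, and 7.6.1 mixes two dating rules.

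- **Confirmation dating alone:** about 0.1 to 0.6 points low out of 10, assuming a flat hazard, 5% vs 15%, 10% to 40% of failures needing confirmation, and reading at day 1096. With a linearly rising hazard the 36-month visit carries more: 0.85^0.694 − 0.85 = 4.33 and 0.95^0.694 − 0.95 = 1.50 (0.694 = 0.833²), a contribution of 2.83, so 0.3 to 1.1 points.
- **Actual visit dates as well:** about 0.3 to 1.3 points low in total with symmetric or late 36-month visits (the upper end includes half of failures needing confirmation). With early visits and completers censored at the visit, the scatter error ranges from none to about 0.9 points high. The sign is not determined by the protocol.
- **Scale:** by the formula under Table 5, the standard error is √[(0.0475 + 0.1275)/222] = 2.8 points, so the shift is well under one standard error.

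A reader might also infer that the primary comparison is compromised. It is not: all qualifying failures remain events in the Cox model, and the hazard ratio and power change little.

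**What to change.** In section 7.6:

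- Still count only confirmed failures, but date each at the scheduled visit where criteria were first met. This is the rule 7.6.1 already uses.
- Leave children lost before confirmation censored, as now, and leave the dating of failures by non-randomized treatment as 7.6 states it.
- Estimate the adjusted difference and its 95% CI at nominal month 36, so that every confirmed failure first met at the 36-month visit is included. Censor event-free completers at nominal month 36, after events.
- Keep the confirmation-date version as a sensitivity analysis.

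The cost is wording only, since all visit dates are already collected. The downside is that event times become grouped at the scheduled visits, so a tie-handling method (for example Efron) must be named.
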